11. Patients at risk of developing or having reactivation of syphilis or tuberculosis (e.g. patients with known exposure to or history of syphilis or tuberculosis). Testing for syphilis and tuberculosis will be done at Screening unless such testing has been performed in the past 6 months prior to Screening with documented negative result. Testing should be done per local clinical practice (for syphilis e.g. by positive rapid plasma reagin (RPR); for tuberculosis** e.g. skin test or blood test as per local practice).

NOTE: The Investigator may consult with an infectious disease expert if e.g. test results are unclear or there is suspicion of false positive test results. If the infectious disease expert considers the test results false positive and not clinically relevant, the Investigator must document (in source data and as a comment in the electronic case report form (eCRF)) that the test results are considered false positive and may then randomize the patient.

12. Patients at risk of developing or having reactivation of hepatitis: Positive results at Screening for serological markers for hepatitis (H) A, B, C, and E indicating acute or chronic infection:
 - anti-HA Immunoglobulin (Ig) M (IgM)
 - HBs Ag and/or anti-HBc IgM and/or HB virus deoxyribonucleic acid (DNA)
 - anti-HBs negative and Anti-HBc positive
 - anti-HC IgG (if positive IgG, HCV-RNA PCR will be performed and if negative, patient can be randomized)
 - anti-HE IgM (if positive IgG and/or IgM, perform HE-RNA PCR and if negative, patient can be randomized)

NOTE: If the Investigator suspects false positive hepatitis serology results, such as an antibody pattern indicating acute hepatitis infection but no corresponding elevated liver enzymes and no signs or symptoms of liver disease, an infectious disease expert may be consulted. If the infectious disease expert finds no evidence of acute or chronic hepatitis infection and considers the serology results false positive and not clinically relevant, the Investigator must document (in source data and as a comment in the eCRF) that the serology results are considered false positive and may then randomize the patient.

13. Have received any live or live-attenuated vaccines (including for varicella-zoster virus or measles) within 2 months prior to randomization

14. Have been treated with any of the medications listed below (Note: no wash-out period is required in the case of prior treatment with interferon- β or glatiramer acetate):

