5.3 Treatment assignment and randomization

Eligible patients will be randomized in a 1:1 ratio to either the active ofatumumab 20 mg group or to the active teriflunomide 14 mg group. The randomization will be stratified by geographical region and by MS subtype (RRMS, SPMS). Study sites can only participate in one of the 2 studies to ensure independence of each study.

On Day 1 (randomization visit), all eligible patients will be randomized via Interactive Response Technology (IRT) to one of the treatment arms. The Investigator or his/her delegate will contact the IRT after confirming that the patient fulfills all the inclusion/exclusion criteria. The IRT will assign a randomization number to the patient, which will be used to link the patient to a treatment arm and will specify a unique medication number for the first package of investigational treatment to be dispensed to the patient. The randomization number will not be communicated to the caller.

The randomization numbers will be generated using the following procedure to ensure that treatment assignment is unbiased and concealed from patients and Investigator staff. A patient randomization list will be produced by the IRT provider using a validated system that automates the random assignment of patient numbers to randomization numbers. These randomization numbers are linked to the different treatment arms, which in turn are linked to medication numbers. A separate medication list will be produced by or under the responsibility of Novartis Drug Supply Management using a validated system that automates the random assignment of medication numbers to packs containing the investigational drug(s).

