6.5.4.4 Other

Testing of lab samples will be conducted at Screening to determine the patient's eligibility for inclusion in the study with respect to hepatitis and HIV viruses, total IgG and IgM serology status. Testing for syphilis and tuberculosis at Screening is needed unless such testing has been done in the past 6 months with documented negative results (see Exclusion criterion 11, [Section 4.2](#)). If sites don't have the possibility to test tuberculosis locally, Quantiferon®-TB Gold test may be requested to be done by the Central laboratory to assess patient's eligibility.

A positive result for any of the following serological markers for hepatitis A, B, C, and E indicating acute or chronic infection is an exclusion criterion:

- anti-hepatitis A virus IgM

- hepatitis B surface antigen and anti-hepatitis B core antigen IgM/IgG, HBV-DNA PCR: if negative, patient can be included
- anti-hepatitis C virus IgG (if positive IgG, HCV-RNA PCR will be performed: if negative, patient can be included)
- anti-hepatitis E virus IgM (positive IgG and/or IgM: do HEV-RNA PCR: if negative, patient can be included).

NOTE: If the Investigator suspects false positive hepatitis serology results, such as an antibody pattern indicating acute hepatitis infection but no corresponding elevated liver enzymes and no signs or symptoms, an infectious disease expert may be consulted. If the infectious disease expert finds no evidence of acute or chronic hepatitis infection and considers the serology results false positive and not clinically relevant, the Investigator may document (in source data and in a CRF comment) that the serology results are considered false positive and randomize the patient.

Samples will additionally be collected during the study according to [Table 6-1](#) and [Table 6-2](#) for:

- total IgM and IgG levels
- teriflunomide plasma levels

For study blinding purpose, the results of these tests will not be included as part of the laboratory reports provided to the Investigators or Sponsor study team during the study. Teriflunomide levels will be assessed by personnel not otherwise involved in the study for the purpose of determining if continued follow up is required ([Section 3.1](#)). IgM and IgG levels will be assessed by personnel, not otherwise involved in the study, for the purpose of safety and guidance provided in [Appendix 3](#) should be followed.

Additional samples for PK, ADA, [REDACTED] will be taken ([Sections 6.6.2](#) to [6.6.5](#))

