In oncology patients treated with ofatumumab, cases of fatal hepatitis B virus (HBV) reactivation and fatal infection due to hepatitis B in patients who have not been previously infected have occurred (refer to local ARZERRA[®] prescribing information). The MS patients enrolled in the study who are at potential risk of HBV reactivation (e.g. patients with evidence of prior HBV infection (anti-HBc positive and HBsAg negative) and whose HBV DNA test is negative at Screening, should be closely monitored for signs of active HBV infection or reactivation during the study. In patients with suspicion of HBV infection (active/reactivation), laboratory testing for HBV should be done. For patients who show evidence of hepatitis B infection (HBsAg positive [regardless of antibody status] or HBsAg negative but anti-HBc positive), the Investigator is advised to consult with physicians with expertise in managing hepatitis B regarding monitoring and consideration for HBV antiviral therapy.

In patients who develop reactivation of HBV while receiving study drug, immediately discontinue study drug and institute appropriate treatment and follow up.

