2.8.3.3 Serology at screening

Collected data of laboratory serology to determine patient’s eligibility includes parameters with respect to hepatitis and HIV viruses. Parameters with respect to hepatitis include 1) anti-hepatitis A virus IgM; 2) hepatitis B surface antigen and anti-hepatitis B core antigen IgM/IgG; 3) anti-hepatitis C virus antibody; 4) anti-hepatitis E virus IgM.

The result of each serology parameter is a categorical value. The number and percentage of patients with values in each of the categories will be provided by treatment group for all above mentioned parameters. Serology test should be performed once at screening. For patients with

multiple assessments, the latest result will be used in the summary. Additional serology data with numerical values may be collected but will not be reported.

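### Protocol Section 6.5.4.4 restates the hepatitis B exclusion so that it disagrees with exclusion criterion 12, and its PCR clause is most naturally read as admitting patients whom criterion 12 bars

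*Protocol*

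**What the plan says.** Protocol Section 4.2, criterion 12, has two hepatitis B lines. The first excludes on a positive result for "HBs Ag and/or anti-HBc IgM and/or HB virus deoxyribonucleic acid (DNA". The second excludes a patient who is "anti-HBs negative and Anti-HBc positive". Neither carries a PCR exception. The hepatitis C and E lines of the same criterion do: "anti-HC IgG (if positive IgG, HCV-RNA PCR will be performed and if negative, patient can be randomized", and "anti-HE IgM (if positive IgG and/or IgM, perform HE-RNA PCR and if negative, patient can be randomized".

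Section 5.3 makes these criteria the gate to treatment: the site contacts the randomization system "after confirming that the patient fulfills all the inclusion/exclusion criteria".

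Section 6.5.4.4 lists hepatitis markers again, introduced as results that exclude a patient. Its hepatitis B bullet is: "hepatitis B surface antigen and anti-hepatitis B core antigen IgM/IgG, HBV-DNA PCR: if negative, patient can be included".

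Section 15.2 (Appendix 3) reports, in oncology patients given ofatumumab, "cases of fatal hepatitis B virus (HBV) reactivation and fatal infection due to hepatitis B". It asks for close monitoring of enrolled patients with evidence of prior infection who are anti-HBc positive, HBsAg negative and HBV DNA negative at screening. It does not give their anti-HBs status.

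SAP Section 2.8.3.3 lists the screening serology to be summarized. Its hepatitis B entry follows the Section 6.5.4.4 markers: "hepatitis B surface antigen and anti-hepatitis B core antigen IgM/IgG; 3) anti-hepatitis C virus antibody". Neither anti-HBs nor HBV DNA is named.

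**The concern.** Two sections of the current protocol claim to define the same hepatitis B exclusion and do not agree. The Section 6.5.4.4 bullet omits anti-HBs, which criterion 12 needs; adds anti-HBc IgG, which criterion 12 does not treat as excluding by itself; and ends with a permission to include that criterion 12 does not contain for hepatitis B.

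The patient most clearly affected has an isolated positive anti-HBc IgG: HBsAg negative, anti-HBs negative, HBV DNA negative. Criterion 12 has a line written for this patient and excludes them. A site that treats the Section 6.5.4.4 bullet as a PCR exception would enrol them and, if randomized to ofatumumab, expose them to the reactivation risk that criterion 12 exists to avoid. About 300 centers are to apply this text.

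The difference is not left over from superseded text. For these sections the amendment log records hepatitis C changes and no hepatitis B change.

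**Working it through.** The plan gives no figure to reproduce. The check compares the two rules over every combination of five markers, each positive or negative: HBsAg, anti-HBc IgM, anti-HBc IgG, anti-HBs and HBV DNA. That gives 2^5 = 32 patterns. One assumption is needed: in criterion 12, anti-HBc positive means IgM or IgG positive.

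**Criterion 12.** A patient is admitted only if HBsAg, IgM and DNA are all negative, which leaves 2^2 = 4 combinations of IgG and anti-HBs. The second line then removes IgG positive with anti-HBs negative. So 3 patterns are admitted (all negative; anti-HBs positive only; IgG and anti-HBs both positive) and 32 − 3 = 29 are barred.

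**Section 6.5.4.4.** The bullet is ambiguous, so three readings were counted.

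| Reading of the bullet | Admits | Admits but criterion 12 bars | Bars but criterion 12 admits |
|---|---|---|---|
| A: a negative PCR overrides all serology | 2^4 = 16 | 16 − 3 = 13 | 0 |
| A2: a negative PCR overrides anti-HBc only; HBsAg positive still excludes | 2^3 = 8 | 8 − 3 = 5 | 0 |
| B: any positive HBsAg, IgM, IgG or DNA excludes | 2 | 0 | 1 |

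Under A and A2 all 3 patterns that criterion 12 admits are also admitted, so the subtraction counts the conflicts directly. Under B the pattern wrongly barred is IgG positive and anti-HBs positive with everything else negative. DNA-positive patients are excluded under every reading and under criterion 12.

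**Why no reading of the listed markers can match.** Take two patients who are IgG positive and negative for HBsAg, IgM and DNA, one anti-HBs positive and one anti-HBs negative. Criterion 12 admits the first and bars the second. The bullet does not use anti-HBs, so any rule built from its markers treats both alike and must be wrong for one of them.

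**Which reading is more natural.** Two features favor the admitting reading.

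- The hepatitis C and E bullets directly below use the same closing phrase, and there it plainly means that a negative PCR rescues positive serology.
- Under reading B every anti-HBc positive patient would be excluded, apart from results that an infectious disease expert declares false positive. The prior-infection group that Section 15.2 says to monitor would then be essentially empty.

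Section 15.2 does not itself conflict with criterion 12, because the monitored patients can be those who are anti-HBs positive.

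**The case against.** The strongest reply is that the operative rule is not in doubt. Section 4.2 excludes anyone meeting any listed criterion, Section 5.3 requires all criteria to be confirmed before randomization, and a laboratory section cannot waive an exclusion. Enrolling a barred patient would be a protocol deviation. This stands, and it is why Section 6.5.4.4 is the text to correct. It does not make a contrary instruction harmless, and the hepatitis list in Section 6.5.4.4 has no pointer to criterion 12, although the same section refers to criterion 11 for syphilis and tuberculosis.

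A second reply is that the lead-in makes any positive marker excluding, and that the hepatitis B bullet lacks the explicit trigger to run a PCR found in the hepatitis C and E bullets, so reading B is available. It is available, and it carries no safety risk. But the hepatitis C and E bullets sit under the same lead-in and still allow a PCR rescue, and reading B does not match criterion 12 either.

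Third, there are safeguards. Section 8.1 requires monitors to verify adherence to the eligibility criteria in full; Section 15.2 adds monitoring and immediate discontinuation on reactivation; Section 5.6.2 requires permanent discontinuation. These limit the harm, but the last two act after exposure and monitors may find the error only after randomization. The false-positive note in both sections needs an infectious disease expert's judgment and is not an automatic PCR exception.

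Fourth, the SAP lists all data (Section 2.1) and summarizes protocol deviations (Section 2.3.1), so the affected patients could be found there. That is fair; the gap is confined to the serology summary.

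Finally, counting patterns gives rare combinations the same weight as common ones. That is also fair, and the counts say nothing about how many patients are affected.

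**Conclusion.** The concern holds. Section 6.5.4.4 does not reproduce criterion 12 under any reading of its listed markers. Depending on the reading, it admits 13, 5 or 0 of the 29 patterns that criterion 12 bars, and in the last case it bars 1 of the 3 that criterion 12 admits. The clinically clear case is isolated anti-HBc IgG positive, anti-HBs negative, DNA negative.

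The counts rest on reading anti-HBc positive in criterion 12 as IgM or IgG. The preference for the admitting reading is a judgment from the parallel bullets and Section 15.2; the mismatch does not depend on it. The documents give no marker frequencies, so no number of affected patients can be stated, and nothing in them shows that anyone was wrongly enrolled.

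This is an eligibility and safety wording error that should be corrected. It has no bearing on type I error, power, endpoints, analysis sets or the efficacy analysis.

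**What to change.** Replace the hepatitis B bullet in Protocol Section 6.5.4.4 with criterion 12's two lines (exclude if HBsAg, anti-HBc IgM or HBV DNA is positive; exclude if anti-HBc is positive and anti-HBs is negative), or with a cross-reference to criterion 12. Do not include a negative-PCR exception. If the sponsor's clinical experts want one for hepatitis B, it should be decided deliberately and written into criterion 12 itself.

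Two optional additions would help: state in Section 15.2 that the monitored prior-infection patients are those who are anti-HBs positive, and add anti-HBs and HBV DNA to the serology summary in SAP Section 2.8.3.3.

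The cost is a wording amendment to one bullet, plus the optional clarification in Section 15.2 and a small addition to one SAP table. Sample size, endpoints and analysis sets do not change.

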6.5.5 Electrocardiogram (ECG)

An ECG will be performed in this study as part of the eligibility assessment and at end of treatment/end of study. Additional unscheduled ECGs may be performed at Investigator's discretion if clinically indicated.

Single 12 lead ECGs are collected. The ECG should be recorded (after 10 minutes rest in the supine position to ensure a stable reading) according to the local site practice. Clinically significant ECG findings at Baseline must be discussed with the Sponsor before administration of study treatment.

The preferred sequence of cardiovascular data collection during study visits is ECG collection first, followed by vital signs, and blood sampling. The Fridericia QT correction formula (QTcF) should be used for clinical decisions.

The original ECGs on non-heat-sensitive paper / and a certified copy on non-heat sensitive paper), appropriately signed, must be collected and archived at the study site. Each ECG tracing must be labeled with study number, subject initials, subject number, date and time, and filed in the study site source documents.

Findings and clinically significant abnormalities must be recorded on the relevant section of the Medical history/Current medical conditions and AE CRF page as appropriate.

6.5.6 Pregnancy and assessments of fertility

Serum pregnancy tests will be conducted for all women who are of child bearing potential at the Screening, EOT and EOS Visits. Urinary pregnancy tests will be conducted for all women who are of child bearing potential at all other scheduled clinic visits as indicated in Table 6-1 and Table 6-2. In addition, the women will be provided with urinary pregnancy test kits for monthly home pregnancy testing required between the scheduled 3-monthly clinic visits. The patients will document the date and result of each home pregnancy test in a diary provided for the study. A monthly structured telephone interview (Table 6-1) will also be conducted with the patients which includes questions to confirm that the home urine pregnancy testing was done and the result. In the case of a positive test result the patient must contact the Investigator immediately for confirmatory testing at the Investigator's discretion.

In addition, the Investigator will review the contraception status with the patient at each visit per Table 6-1 and Table 6-2 to ascertain that the patient continues to comply with protocol requirements for highly effective contraception as applicable.

6.5.7 Appropriateness of safety measurements

The safety assessments included in this study (Table 6-1) are standard for the MS indication and study patient population and appropriate based on the current safety profile of ofatumumab iv and sc (Investigator's Brochure) and the teriflunomide (Aubagio®) prescribing information.

The use of an instrument such as the C-SSRS to detect suicidal ideation or behavior is currently mandated in studies of CNS active drugs.

[figure not shown]
6.6 Other assessments

MS is associated with a variable combination of symptoms, including sensory loss, imbalance, mobility loss, bladder and bowel dysfunction, cognitive dysfunction, spasticity, pain, and sexual dysfunction. Measurement of these wide-ranging effects of MS on the lives of patients is beyond the scope of the clinician assessed endpoints commonly used to evaluate therapeutic effectiveness in MS studies. Patient-reported outcome measures [REDACTED] are included in this study to provide an empirical assessment from the patient's perspective of the benefits of treatment that cannot be gained from MRI, EDSS, or relapse measurement.

Samples for PK, immunogenicity potential (ADA), [REDACTED] [REDACTED] will also be assessed and evaluated as applicable in relation to efficacy, safety data and population under study.

[REDACTED]

[REDACTED]

[figure not shown]
[figure not shown]
6.6.2 Pharmacokinetics

PK trough values at steady state for ofatumumab will be used to conduct a population pharmacokinetics analysis. Sampling time points are provided in [Table 6-1](#). Samples for PK assessment should be taken prior to dosing at the Month 1 visit. For any later PK visits, if the visit coincides with the day the monthly injection is scheduled, the patient should not take the injection in the morning before coming to the site so that the PK sample can be drawn before the injection. The PK sample collection date and time must be entered on the appropriate CRF.

Further details on sample collection, numbering, processing and shipment will be provided in the Laboratory Manual provided to the sites.

